Infants acquire passive immunity to measles and rubella by transplacental transfer of maternal antibodies. (7, 8) These antibodies offer some protection for infants prior to receipt of MR vaccine. Mothers who have had natural infection in the past typically have higher titers of antibodies compared with women who have vaccine-induced antibodies and because of their lower titer, vaccine-derived maternal antibodies transferred to the infant decline to an undetectable level sooner than naturally-derived maternal antibodies. This has been documented by researchers who tested paired mother and infant serum samples for measles and rubella antibodies [1, 2] (some studies included blood samples drawn at week 36 of pregnancy and cord blood sample) [3, 4]. They reported that infants of vaccinated women have significantly lower antibody concentrations than did infants of naturally immune women, and infants of vaccinated women lose protective levels of antibodies sooner (i.e., by 6-8 months) than infants of naturally immune women [4].

A study in Matlab, Bangladesh(22) reported that in 1993, 67% of infants by age 5 months and 95% of infants by age 8 months had measles antibody titers below the threshold for protection leaving them susceptible to natural infection. As a result, a rising trend of measles cases below the eligible age of first routine measles vaccination, typically 9 or 12 months of age, has been observed. From 2004-2006, in Bangladesh an increase in the proportion of measles cases among infants <9 months of age was noted in

6 selected outbreaks. In these outbreaks 54% of cases were 6-8 months of age. From 2002-2009, 10% of confirmed measles cases in WHO African Region occurred among infants <9 months of age(23). In China, measles cases have been noted to have a bimodal distribution with majority of the cases either in adults up to age 30 in infants younger than 8 months, the routine age of first dose of measles vaccine. To improve the accuracy of interpretation of study results it would be prudent to test mothers of enrolled infants for measles and rubella antibodies. This will also enable us to determine the proportion of mothers with undetectable, detectable and protective levels of antibodies, and to assess the relationship between the level of antibodies in mothers and their infants' maternal antibodies.

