This study will be an open-label, randomized, 2-arm clinical trial. 620 children will be enrolled and randomized at 6 months of age to one of two study arms. The primary objectives of this study are to assess the immunogenicity of MR vaccine at 6 months, and assess equality of MR vaccine seroconversion administered at 9 months following administration of an earlier MR vaccine dose at 6 months of age compared with MR vaccine dose administered at 9 months only without previous MR vaccination. The study will enrol generally healthy 6 month old infants living in Matlab and who have never received an MR vaccine dose and have no history of measles or rubella. Participants will be followed to 11 months of age.

Infants in this study will be randomly assigned to one of two arms. Infants in Study Arm A will receive MR vaccine at 6 months of age (at enrolment) and at 9 months. Infants in Study arm B will receive MR vaccine only at 9 months.

Blood specimens will be collected from all infants at 6, 9 and 11 months of age. The 6 month sample is a pre-vaccination sample and mainly will be used to determine maternal antibody levels. For arm A, the sample collected at 9 months before the second MR dose will be used to assess antibody levels after the first MR dose at 6 months of age. For study Arm B, the 9 month sample will be used to assess measles and rubella antibody decay rate. The sample collected at 11 months will be used to assess immune response to either a two dose or a one dose schedule (arms A and B, respectively). The study design and participant evaluations are illustrated in the Table.

Table: Schematic representation of study arms

Arm		Age of participant				
		6 months	9 months	11 months	Sample size	Enrollment target (sample size + 10% attrition)
A	MR 6 & 9 months	MR •	MR •	•	279	310
B	MR 9 months	•	MR •	•	279	310
	Total (infants)				558	620
	Mothers	•			558	620

• Indicates blood collection
MR- Measles -rubella vaccination

Blood specimens will be collected from mothers of all enrolled infants at time of enrolment.

Study enrolment and withdrawal

A sample of 620 infants at age 6 months (180 days, +/- 7 days) of age (310 per each study arm) will be enrolled from population living in Matlab area. Inclusion and exclusion criteria are provided below.

Inclusion criteria: Infants

- Healthy infants at 6 months (180 days, +/- 7 days) of age (calendars will be provided to staff)

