For participants in the study group A, the immune response to the 6 month MR dose will be measured at 9 months (blood drawn during the second visit) to evaluate both the proportion seroconverting (from negative to protected), 4-fold or greater increase in antibody titers among pre-vaccination seropositives, after adjusting for decline in maternal antibodies, as well as the magnitude of the immune response (expressed as geometric mean titers of the antibody response). The rate of decay of maternal measles and rubella antibodies will be calculated in infants in arm B based on the difference of antibody levels measured at 6 months (baseline) and 9 months. We will incorporate the model of maternal measles and rubella decay for infants in arm A to measure post-vaccine antibody levels and impact of the maternal

antibody to immune response in infants who had measles or rubella antibodies at enrolment. In the recently published study from Bangladesh, baseline measles virus serum neutralizing antibody seroprotection and anti-rubella virus IgG seroprotection at 9 months of age was low (0.42-1.25% and 0-0.42%, respectively) (21). If during this study, we determine that most children have no detectable levels of maternal measles or rubella antibodies at 6 months it would be impossible to calculate the decay. In this case, we will refer to antibody decay rates reported elsewhere (29, 30).

THE FOLLOWING CHANGES ARE MADE TO THE PROTOCOL:

Since the inception of the project and completion of the field data collection a newer assay, multiplex bead assay (MBA) for measles and rubella has been developed. It has been validated by the CDC measles and rubella laboratories.

Multiplex Bead Assay (MBA) for Serum Antibody Detection of Measles and Rubella

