- Collection of blood from mothers at time of enrolment to assess measles and rubella titers, as only one blood sample will be collected. (To assess the proportion of mothers with undetectable, detectable and protective levels of measles and rubella antibodies)
- Time from randomization to 9 and 11 months (To assess the correlation between measles and rubella antibody levels in women and levels of maternal antibodies in infants)
- Time from randomization to 9 months, Arm B (To estimate the half-life of decay of maternal measles and rubella antibodies in infants)

The primary end-point assessment is based on measles titers by MBA (mIU/ml) and rubella titers (IU/mL) by ELISA on sera collected 12 weeks after the first dose (time between 6 and 9 months) and 8 weeks after completion of vaccination (time between 9 and 11 months). Immune response is defined as a 4-fold increase in antibody titers 12 weeks after vaccination (post-6-month visit) compared with 6-month pre-vaccine titers accounting for the expected decline in maternal antibody titers or a change from antibody-negative to positive (i.e. seroconversion). However, quantitative data (i.e., determining titers) will allow seroconversion defined by other -fold increases to also be assessed.

We will calculate the rate of decay for those infants that have maternal antibodies detected at enrolment (at 6 months) in arm B (anti-measles or anti-rubella IgG levels at 6 months vs 9 months). We will incorporate the model of maternal decay for infants in arm A to measure post-vaccine antibody levels and impact of the maternal antibody to immune response. However, if we determine that most children have no detectable levels of maternal measles or rubella antibodies at 6 months it would be impossible to calculate the decay rate (in Arm B). In this scenario, we will refer to antibody decay rates reported elsewhere (29, 30).

Outcome measures/variables:

The primary end-point assessment is based on measles titers by MBA (mIU/ml) and rubella titers (IU/mL) by ELISA on sera collected 12 weeks after MR 6-month dose of vaccination (i.e., at 9 months) for study Arm A.

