Immune response is defined as a 4-fold increase in antibody titers 12 weeks after vaccination (post-6-month visit) compared with 6-month pre-vaccine titers accounting for the expected decline in maternal antibody titers or a change from antibody-negative to positive (i.e. seroconversion). In addition, quantitative data on antibody titers will allow us to assess the magnitude of seroresponse show as $-N$ -fold increases of pre- and post-vaccine titers. Seroprotection is defined as titer of ≥ 120 mIU/mL for measles and rubella >10 IU/mL

Secondary outcomes:

Several secondary outcomes will be assessed:

- 1) Secondary outcome is based on measles titers by MBA (mIU/ml) and rubella titers (IU/mL) by ELISA on sera collected 8 weeks after MR 9-month dose of vaccination (i.e., at 11 months) – post two dose series for participants in Arm A and 1 dose for arm B.
- 2) The safety profile of MR vaccine will be assessed by incidence of specific symptoms/problems. They will be categorized into one of the following three categories:
 - a) Immediate reactions (with emphasis on allergic reactions), occurring in the first 30 minutes post vaccination observed by study staff at the fixed site clinic.
 - b) Adverse events (AE) following 6-month MR dose that may occur during the 48 hours after 6-month MR vaccine administration. AEs will be graded and subcategorized as those deemed related to vaccination or not by the investigator.
 - c) Serious adverse events (SAEs) occurring from vaccination during the course of the study, identified or observed by study staff and/or reported by parent at any time during the study period. SAEs will be subcategorized as those deemed related to vaccination or not by the investigator and reviewed by the local Data and Safety Monitoring Board (DSMB) and icddr,b ERC committee.

Data Analysis

This is an open-label trial clinical trial that compares immunogenicity of MR vaccine schedules. The study will recruit 620 participants in 2 arms. Participants will be enrolled at 6 months of age and followed at 9 months and 11 months of age for a total of 5 months of follow-up.

General analytical issues

The data will be analysed by study investigators that include epidemiologists and statisticians. Statistical packages that would be used for the analysis include R, SAS and STATA.

The immunogenicity of each MR vaccination schedule will be determined by measuring antibody levels:

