- Compare the proportion of participants demonstrating seroconversion at 9 months in both study arms. We will use chi-square test to test for statistical significance
- Compare the change in median titers of measles and rubella antibodies by study arm
- Compare immunogenicity of MR vaccine administered at 6 months (Arm A) vs 9 months (Arm B). Analyse the relationship of infants' immunogenicity to MR vaccine and mothers' level of antibodies
- Analyse the relationship between the levels of infants' maternal measles and rubella antibodies and mothers' antibodies
- Analyse results of adverse events by study arm and compare by age and arm of the study.

Data Safety Monitoring Plan (DSMP)

Records to be kept

Participant data will be collected using case report forms (CRFs). Personal identifiers will not be recorded on any CRFs, biological specimens or electronic records. Participants will be identified by a participant identification number (PID), which will be provided after enrolment and randomization. The PID will be used to link information recorded in CRFs and results from laboratory analysis of biological specimens.

Data entry, cleaning and storage

Records of participants will be kept in a locked cabinet with access restricted to study staff and investigators. All computer records will be kept in a locked room. The computers will be password protected. Only the study staff and investigators will be authorized to access the digital records.

Data from the CRFs will be entered into an electronic database. Checks will be performed to identify and correct data entry errors. After the completion of analysis and publication of study results, the study forms and database will be archived. The forms will be stored in a locked cabinet with access restricted to investigators. The database will be password protected.

Site monitoring plan

Prior to start of the study, Standard Operating Procedures (SOPs) will be developed by investigators in consultation with study staff. Study staff will be trained in study procedures and human subjects' management. After start of the study monitoring of study site will be conducted twice.

During these monitoring visits the following study documents and procedures would be reviewed:

1. Participant records, including consent forms
2. CRFs and other supporting data
3. Adverse event forms
4. Data Safety and Monitoring Board (DSMB) reports
5. Laboratory specimen records
6. Vaccine and biological materials storage and records

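### Arms are compared on change in median titre with no visits named; a log-titre comparison adjusted for the 6-month sample would be well defined and usually more precise

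*Combined protocol and SAP*

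**What the plan says.** The list of planned comparisons that closes the Secondary analytical approach section includes: "Compare the change in median titers of measles and rubella antibodies by study arm". No other line in that list names titres as the quantity compared between arms. It does not say which visits define the change, whether it is a change in group medians or a median of individual changes, or what test or interval applies.

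Two other sections describe magnitude differently. Special Assays or Procedures has Arm A's response to the 6-month dose "expressed as geometric mean titers of the antibody response". Outcome measures/variables says that "quantitative data on antibody titers will allow us to assess the magnitude of seroresponse", shown as N-fold increases.

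On the samples themselves, Study design states: "The 6 month sample is a pre-vaccination sample and mainly will be used to determine maternal antibody levels". The second sample has a different status in the early-dose group, because there "the sample collected at 9 months before the second MR dose will be used to assess antibody levels after the first MR dose". Undetectable baselines appear only as a contingency (Time to endpoint): "if we determine that most children have no detectable levels of maternal measles or rubella antibodies at 6 months", published decay rates will be used.

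**The concern.** Titres are the sensitive measure of whether the 6-month dose alters the later response. The Measles-rubella vaccine section cites 100% rubella seroprotection after a 9-month dose in Bangladesh. If that recurs, proportions cannot separate the arms for rubella, and the titre comparison carries the information.

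The planned comparison is not defined, and each reading that uses the 11-month titre has a weakness. A change from 6 months removes a maternal titre from a vaccine-induced one. A change from 9 months starts Arm A from a titre that its own treatment has already altered. The one sample taken before any study vaccine in both arms, at 6 months, is not used to adjust the between-arm titre comparison. With three magnitude summaries in the text of an open-label trial, there is also room to choose among them after seeing results.

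**Working it through.** **Inputs.** The documents give no titre SD, no correlation between visits, no share of undetectable 6-month titres and no power for titres, so those values are assumed below. The stated 279 per arm is for 75% against 65% seroconversion. It reproduces exactly as one-sided 5% with continuity correction, does not bear on titres, and serves here only as the arm size.

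**1. Which visits?**
- *6 to 11 months.* The Background section on measles vaccines, Response to early vaccination and Study Rationale all expect maternal antibody to reduce response. The baseline should therefore correlate negatively with the 11-month titre, which makes subtraction worse and adjustment more useful.
- *9 to 11 months.* Let both arms end at titre T, from starting titres S_A and S_B. The ratio of fold rises is (T/S_A)/(T/S_B) = S_B/S_A. This is below 1 whenever Arm A responded to its first dose, although the final titres are identical.
- *6 to 9 months.* This sets Arm A's response against Arm B's decay. It is coherent, but silent on the 9-month dose.

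**2. Share above the cut-off at 6 months.** Passive immunity reports for 1993 that "67% of infants by age 5 months and 95% of infants by age 8 months had measles antibody titers below the threshold for protection". Linear interpolation gives 67 + (95 − 67) × (6 − 5)/(8 − 5) = 76% below, so about 24% above. This is the protective threshold, used here as a stand-in for the assay floor.

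**3. Cost of subtracting.** With k = SD(baseline)/SD(post) and correlation ρ on the log scale, the variance of a mean change relative to baseline adjustment is (1 + k² − 2ρk)/(1 − ρ²).
- Equal SDs (k = 1): 2/1 = 2.0 at ρ = 0; 2.4/0.96 = 2.5 at −0.2; 1.6/0.96 = 1.67 at +0.2.
- 24% above the floor: take a standard normal baseline floored at 0.706 SD, and post-vaccination SD 1. The floored variance is 0.120, so k = 0.347, and the correlation shrinks by 0.24/0.347 = 0.69. At ρ = 0 the ratio is 1.12. At −0.2 it is (1 + 0.120 + 2 × 0.139 × 0.347)/(1 − 0.139²) = 1.24.
- For group medians the cost is nil. With most values at the floor, each arm's baseline median is the same constant.

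**4. Cost of the median.** For normal log titres the variance ratio of median to mean is π/2 = 1.57, so 279 per arm performs like 279 × 2/π = 178.

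**5. Simulation.** 279 per arm, 2,000 runs, response SD 1 on the log scale. Entries are variance relative to the baseline-adjusted log-titre comparison, with floor values entered as they stand.

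| 6-month titres above floor | ρ | Non-responders at floor | Mean change | Change in group medians | Median of individual changes |
|---|---|---|---|---|---|
| 100% | 0 | none | 1.88 | 2.91 | 2.96 |
| 70% | −0.3 | none | 2.19 | 4.14 | 3.57 |
| 33% | 0 | none | 1.20 | 1.56 | 1.78 |
| 33% | −0.3 | none | 1.48 | 1.66 | 2.12 |
| 10% | −0.3 | none | 1.14 | 1.71 | 1.81 |
| 33% | −0.3 | 25% | 1.07 | 0.86 | 1.17 |
| 10% | −0.3 | 25% | 1.04 | 0.84 | 0.91 |

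At 24% above the floor with log-normal responses, median-based changes came to about 1.55 to 1.75. With 25% non-responders at the floor, the group-median ratio ran from 0.6 to 2.3, depending on the gap between responders and floor.

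**The case against.** The strongest reply is that the line is underspecified rather than wrong. It may mean 6 to 9 months, where a change is natural. The median is also robust: with a quarter of infants at the floor it can beat the adjusted GMT. The plan assumes 25% to 35% measles non-seroconversion, which strains a log-normal model. The plan does use the 6-month titre, through the maternal decay model. And an 11-month GMT ratio compares two doses with one, so it does not isolate the 9-month dose.

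Most of this stands as a limit on size. It does not remove the need to name visits and one summary, and the decay model serves the response definition in Arm A, not the between-arm titre comparison.

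A reader might go further and infer that the 6-month titre is unrelated to response and mostly undetectable, so that subtracting it doubles the variance or worse. The documents do not support that. They expect a negative relation. The 67% and 95% figures concern protection in 1993, not detection, and undetectable baselines are only a contingency. The two premises also work against each other, since a baseline mostly at the floor has little variance to add. Nor do the GMT and median passages strictly contradict each other: one describes Arm A at 9 months, the other a between-arm comparison.

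**Conclusion.** The concern holds in a limited form. The titre comparison is undefined as to visits, inconsistent with the other two magnitude summaries, and makes no use of the common pre-vaccination sample for adjustment. A 9-to-11-month reading could mislead about blunting.

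With log-normal responses and about a quarter of 6-month titres above the floor, the median-based change has roughly 1.5 to 1.8 times the variance of the adjusted comparison. Subtraction alone costs about 1.1 to 1.2 for a mean change (correlation 0 to −0.2) and nothing for group medians. Factors of 2.0 to 2.5 need a baseline as variable as the post-vaccination titre. All of these rest on assumed distributions. The gain is clearest for rubella, where near-universal response is expected, and is not assured for measles.

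**What to change.** Replace the change-in-median line with a regression of log 11-month titre on arm and log 6-month titre. Report the GMT ratio (Arm A / Arm B) with a 95% CI for each antigen. Fit the same model to the 9-month titre. Treat values below the assay limit as left-censored, and state that limit for each assay. Do not adjust for the 9-month titre, which in Arm A follows treatment. Keep medians by arm and visit as a descriptive or sensitivity result. Describe the 11-month ratio as two-dose against one-dose schedule.

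The cost is plan wording, with no new samples and no change to sample size or the seroconversion analysis. The downside is reliance on a log-normal model. It fits less well for measles if a quarter or more of infants do not respond, and at 9 months, when Arm B is still unvaccinated and may lie largely below the limit. The medians and proportions should be read beside it there. The change should be made before titres are analysed by arm.
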